Proof of hospitalization in a sub-set of participants would be beneficial to validate the primary outcome. Therefore, we will randomly select participants who have been hospitalized for the hospitalization verification sub-study. We will request to access patient medical records for these selected patients. All participants for the trial will be requested to sign the UCSF HIPAA Authorization form for permission to use personal health information for research. We will also use the US National Death Index to link patient deaths to our study.

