3.4.2 Secondary Outcomes

Secondary outcomes will include

- **Hospitalization:** Defined as any visit to the emergency room or other hospital setting that resulted in a stay of 24 hours or more.
- **Adverse events:** we will conduct an adverse event survey at Day 3 after treatment, including gastrointestinal side effects (nausea, vomiting, diarrhea, abdominal pain) and rash. We note that some COVID-19 patients report gastrointestinal symptoms, and this survey will provide data on whether azithromycin causes additional gastrointestinal effects beyond those symptoms.
- **Prevalence of positive swabs:** we will compare the prevalence of SARS-CoV-2 positive swabs at Day 3 after treatment in self-collected nasal, saliva, and rectal swabs in azithromycin compared to placebo-treated participants.
- **Viral load:** we will assess viral load by RT-PCR in self-collected nasal, saliva, and rectal swabs at Day 3 after treatment.
- **Mortality:** we will collect emergency contact/next of kin information during the baseline questionnaire. We will follow-up with the emergency contact if participants are lost to follow-up at the Day 14 questionnaire to assess mortality and hospitalization outcomes.
- **Genetic macrolide resistance determinants:** We will evaluate the prevalence of genetic macrolide resistance determinants *ermB*, *mefA/E*, and *mphA* by targeted PCR in rectal samples collected at Day 3 after treatment.
- **COVID-19 symptoms:** we will ask patients about COVID-19 symptomology during each online questionnaire, including cough, fever, myalgia, anosmia, shortness of breath (and related abilities such as ability to walk across a room or up a flight of stairs), fatigue, conjunctivitis, and orthostatic symptoms.

- **Number of emergency room visits:** during each online questionnaire we will survey patients about any emergency room visits (with stays <24 hours) that occurred since their last survey.
- **Number of household members with COVID-19 (confirmed or symptomatic):** during each online questionnaire we will ask participants how many of their household members have symptoms of COVID-19 or confirmed disease.
- **Death:** we will attempt to link deaths among participants to the National Death Index.

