5.12 Emergency Room Follow-Up

Participants who report an emergency room visit during their follow-up surveys will be re-contacted by the study team by phone or email. The participant will be asked to provide more detail regarding their emergency room visit. The study team member will ask the participant the primary reason for their emergency room visit, which interventions they received, and any other relevant information such as how long they were in the ER for. The participant's responses will be recorded in RedCap.

6 Sample Collection Procedures

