11.3 Serious Adverse Events

A Medical Monitor for the trial will be designated by the study lead investigators. The Medical Monitor will review all SAE's that occur and evaluate the likelihood of an association to the study drug. If deemed possibly related to the study drug by the Medical Monitor, the SAE will be forwarded to the DSMC and IRB if necessary. The Medical Monitor for this study will be [name], an internal medicine and infectious disease specialist at UCSF. The Medical Monitor will review serious adverse event cases ideally within 24 to 48 hours. Other adverse events will be analyzed by arm at the end of the study or per request from the DSMC.

Any serious adverse events will be reported to Pfizer. An ISR SAE Form (Investigator-Sponsored Research Serious Adverse Events Form) will be completed by study personnel for each event and sent to [contact].

An SAE is defined as any adverse event that:

- Results in death
- Is life-threatening (i.e., causes an immediate risk of death)
- Results in persistent or significant disability or incapacity
- Results in a congenital anomaly or birth defect
- Changes the risk/benefit ratio of the study
- Any cardiovascular related or unrelated serious adverse event

Or that is considered to be:

- An important medical event

Serious adverse events will be reported to Pfizer, the Data and Safety Monitoring Board and the Institutional Review Board at the University of California, San Francisco. Any event deemed to be definitely, probably, or possibly related and is serious or unexpected will be reported to the IRB within 5 days. Deaths and life-threatening events will be reported immediately.

UCSF will be responsible for discerning which medical occurrences meet the serious adverse event criteria. UCSF personnel will then fill out an ISR SAE form and submit to Pfizer no later than 48 hours from UCSF's awareness date. UCSF awareness date should be noted on the ISR form. UCSF will report SAEs around the clock, 7 days a week. UCSF should not report duplicate reportings of SAEs and provide the causality determined by the Medical Monitor.

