Serious adverse events will also be reported to the Food and Drug Administration (FDA). UCSF will be in compliance with the FDCA (21 USC 301 et seq) and Title 21 of the code of federal regulations. UCSF will report any unexpected fatal or life-threatening suspected adverse reactions to the FDA no later than 7 days after initial receipt. UCSF will also report SAEs, findings suggesting significant human risk, and/or clinically important events that increase the rate of SAEs within 15 days after determining the information qualifies for reporting. UCSF must always cite the IND number 149526 on all correspondence. Additionally, UCSF will submit an annual progress report within 60 days of the anniversary of the IND active date (4/18/2020).

12 Protection of Human Subjects

The research team will obtain formal ethical approval prior to the study start. Informed written consent will be collected from all participants electronically due to the remote nature of the study. A research team member will describe the study to participants in depth including information about the treatment and study activities. If, at any time, a participant wishes to withdraw from the study, they will be free to do so.

A Data and Safety Monitoring Board (DSMB) will be empaneled to review patient data throughout the course of the study. The Board will meet to review and approve study procedures prior to trial commencement and will review reports of serious adverse events and interim safety and efficacy analyses. Members of the DSMB will have expertise in infectious disease, epidemiology, biostatistics, and randomized controlled trials.

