APPENDIX

Appendix 1: Original manual of procedures

REVISION HISTORY

4/9/2020: Addition of 21 day follow up timepoint, added additional details to the Study Methods Chapter.

4/10/2020: Addition of Pfizer information to Medication Chapter, addition of Chapter 12 Study Monitoring.

4/19/2020: New eligibility criteria added (QT prolongation + chloroquine over 55).

4/20/2020: Chapter 5 and 6: addition of a sub-study where 100 patients per arm are asked to collect nasal, saliva, and rectal swabs at days 3, 7, 14. Addition of chapter 8: Staff responsibilities.

4/21/2020: Addition of adverse events and SAE information per request of Pfizer.

4/24/2020: Addition of Pfizer SAE reporting requirements.

4/27/2020: Addition of section 3.3 Sub-Studies. Addition of Death as a secondary endpoint. Addition of eligibility criteria (not currently taking nelfinavir or warfarin). Section 5.10 change of patient ID number to REDCap based.

4/28/2020: Addition of figure 1 in 3.3. Change in main study swabs from first 300 participants to all participants will be asked to collect rectal swab at day 3.

5/4/2020: Specification that we will exclude pregnant women. Addition of FDA reporting criteria to SAE section.

5/5/2020. Addition of protocol violation section, drug storage section, concurrent medications section

5/6/2020: Specification of cardiovascular related events for reportable serious adverse events to Pfizer

5/12/2020: Removal of rectal swab in group 1 & group 2 in swab sub-study section.

5/26/2020: Addition of [name] and [name] to the protocol. Addition of color-coded sticker scheme for kits to section 5.10. Addition of lot numbers from drug to 10.4.

6/3/2020: Addition of online social media ad campaign under recruitment.

6/8/2020: Expansion of eligibility criteria “positive test within past 3 days” to “positive test within past 7 days”. Specified that participant can fill out questionnaires via email or over the phone in eligibility criteria.

7/8/2020: Addition of unmasking protocol to 3.6.1.

8/24/2020: Addition of protocol for short form method of consent.

9/23/20: Addition of Rhode Island Open Door Health as recruitment site. Addition of EDDM to recruitment methods. Addition of random drawing lottery.

11/13/20: Addition of WebMD to recruiting methods. Addition of language for obtaining informed consent from computer illiterate participants.

12/7/20: Change primary outcome. Moved hospitalization to secondary outcome.

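### The SAE definition does not list hospitalization, and no section sends reported admissions to the Medical Monitor or exempts them as endpoints

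*Protocol*

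**What the plan says.** Protocol 11.3 introduces its list with "An SAE is defined as any adverse event that" and begins it with "Results in death". The other items are an immediate threat to life, persistent or significant disability, congenital anomaly, a change in the study's risk/benefit ratio, a cardiovascular item, and an important medical event. The list is complete on the page, with no redaction or break in it.

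The same section says who acts on the list. University staff decide which occurrences meet the criteria. The Medical Monitor reviews SAEs for a link to the drug. The supplier receives a form for each SAE within 48 hours. Other adverse events are analyzed by arm at the end of the study, or earlier if the DSMC asks.

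Hospitalization appears in 3.4.2 as a secondary outcome: "Defined as any visit to the emergency room or other hospital setting that resulted in a stay of 24 hours or more". It is collected on the Day 7, 14 and 21 questionnaires (3.8, 5.6 to 5.8). Formal questions about adverse events are put at Day 3 only (11.2).

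Two procedures come close to following up an admission. Section 5.12 provides a call-back for emergency room visits: "The study team member will ask the participant the primary reason for their emergency room visit". The answers are recorded in REDCap, and the section goes no further. Section 3.3 provides for medical records on a sample: "we will randomly select participants who have been hospitalized for the hospitalization verification sub-study". Its stated purpose is to validate the trial outcome.

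SAP 6.5 says that all SAEs through Day 21 will be recorded, but it does not define the term.

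**The concern.** In a trial run entirely by mail, telephone and email, a reported admission is the main scheduled signal of serious drug harm after Day 3. Section 11.1 itself lists harms that can lead to admission without an immediate threat to life: hepatitis, cholestatic jaundice, pancreatitis, pseudomembranous colitis, acute renal failure and serious skin reactions. These need not be evident when the Day 3 survey is answered.

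Take a participant admitted for five days with hepatitis who was never in immediate danger and was left without disability. No named criterion clearly covers the case, so it depends on a staff judgment under a term that the protocol does not define. If staff do not make that judgment, nobody is assigned to ask whether the drug caused the event, and no SAE form goes to the supplier. The event would then be missing from the SAE table by arm.

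**Working it through.** No figure in the plan bears on this point, so the check is to read the texts against each other.

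**Step 1. The seven criteria in 11.3, applied to a non-fatal admission of 24 hours or more**

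| Criterion | Can it capture the admission? |
|---|---|
| Death | No, by assumption |
| Life-threatening | Only if there is an immediate risk of death |
| Disability or incapacity | Only if persistent or significant |
| Congenital anomaly | Not relevant to the participant's own admission |
| Changes risk/benefit ratio | Possibly, but this is a judgment about the study more than about one case |
| Cardiovascular item | If cardiovascular; the item is circular, since it uses the term SAE to define an SAE |
| Important medical event | If staff so judge; the term is not defined |

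None of the seven names hospitalization. Five could apply in principle. For an admission outside the first four of those five, the important-medical-event item is the only one left.

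**Step 2. What each recipient receives if that judgment is not made**

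- *Medical Monitor (11.3):* reviews SAEs, so nothing.
- *Supplier (11.3):* receives forms for SAEs, so nothing.
- *IRB (11.3):* a related event that is either serious or unexpected goes within 5 days, so this route stays open without SAE status. It needs a judgment of relatedness, and the only assessor named in the protocol sees SAEs alone. Harms already listed in 11.1 might also be regarded as expected.
- *DSMC (11.3, 15.4):* Closed Reports show secondary endpoints and adverse events by arm, and the DSMC may ask for other adverse events. This is aggregate and mainly tied to meetings. The description does not say that the cause of each admission is shown.
- *FDA (end of 11.3):* mainly SAEs and unexpected fatal or life-threatening reactions, together with findings that suggest significant human risk.

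**Step 3. Is there another link or an exemption?**

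Sections 5.6 to 5.8 and 14.1 collect hospitalization status and say nothing about passing it on. Section 5.12 ends at REDCap and is written for emergency room visits. The record request in 3.3 covers a random sample only. No section says that admissions are left out of SAE reporting because they are an endpoint. SAP 6.5 adds no criterion.

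**Step 4. Workload if admissions were covered**

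The documents give no current admission rate; the revision history says only that hospitalization is much rarer than anticipated. Assume 2% to 4% of the 455 participants:

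- 455 × 0.02 = 9.1, about 9 admissions
- 455 × 0.04 = 18.2, about 18 admissions

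This is the most that the change would add at those rates, because some of these admissions would already qualify under another criterion.

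**The case against.** The strongest case for the plan is that the existing text already catches most of what matters. Staff must identify SAEs among medical occurrences generally, not only among Day 3 answers. Participants may report adverse events at any time (11.2). A serious drug-induced hepatitis is a natural important medical event. All of this is fair. What stands against it is that the outcome rests on discretion, with no instruction to look at the admissions that the questionnaires bring in.

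It can also be said that the follow-up forms are not reproduced and may ask the reason for admission, and that 5.12 arguably covers admissions that came through the emergency room. Both are possible. Neither supplies a route to the Medical Monitor.

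The protocol also commits to federal rules: "UCSF will be in compliance with the FDCA (21 USC 301 et seq) and Title 21 of the code of federal regulations". The content of those rules is not in the documents, so the sentence neither closes the gap nor proves a breach.

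A reader might infer four stronger things, which the documents do not support:

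- *That no safety recipient would learn of such an admission.* The IRB and DSMC routes remain, though they are weaker.
- *That a drug-related admission would be counted as COVID-19 progression.* The definition in 3.4.2 takes no account of cause, so the event stays in an all-cause comparison by arm.
- *That hospitalization was left out because it was once the primary endpoint.* The revision history records "12/7/20: Change primary outcome. Moved hospitalization to secondary outcome" and shows no later change to the SAE section, but nothing states that reason.
- *That the random sample in 3.3 is itself a defect.* It serves outcome validation, not safety.

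**Conclusion.** The point holds as a gap in the route to case-level review. Hospitalization is absent from the SAE definition, and admissions of 24 hours or more are neither sent to the Medical Monitor nor declared exempt. For a non-fatal admission that is not life-threatening, disabling, cardiovascular or risk/benefit-changing, causality review and supplier SAE reporting depend on one undefined, discretionary criterion. The gap does not amount to concealment of harm from every safety body.

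The conclusion rests on the text of 11.3 and on the absence of any linking procedure elsewhere in the protocol or SAP. A questionnaire that already asks the reason for admission would shorten the remedy but would not remove the gap. How many drug-related admissions would be missed cannot be estimated from the documents. The range of 9 to 18 measures all admissions under an assumed rate. Because this is participant safety and the correction is small, it should be made.

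**What to change.** 1. Add one item to the 11.3 list: *requires hospitalization (as defined in 3.4.2) or prolongs an existing hospitalization*.
2. State in 11.3 that each admission reported on the Day 7, 14 or 21 questionnaire goes to the Medical Monitor for a causality assessment. Where the questionnaire does not already give the reason for admission, obtain it by extending the 5.12 re-contact call to hospitalizations.
3. If the sponsor wants admissions judged to be COVID-19 progression kept out of expedited reporting, say so in 11.3 and tabulate them by arm.

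While 11.3 is open, its two statements on what reaches the DSMC and IRB should be reconciled. One forwards SAEs judged possibly related; the other says that SAEs are reported without that condition.

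The cost is one line in the definition, a routing step, some added calls, and at most about 9 to 18 extra Medical Monitor reviews and supplier forms at the assumed 2% to 4% rate. Item 3 would reduce the expedited reports but not the reviews. The gap does not require record retrieval for every hospitalized participant, nor sending all emergency room answers to the Medical Monitor.

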12.1 Institutional Review Board Approval

UCSF Committee on Human Research

UCSF's Committee on Human Research will review the study protocol for ethical approval.

12.2 Informed Consent

As described in section 4.1.1, all participants will electronically sign an informed consent form. Consent scripts will be submitted to the UCSF Committee on Human Research prior to the study start for ethical approval. Young adults and children under 18 years of age, who cannot give

consent by law, will not be included in the study. Participants will be able to ask the research team questions about the study procedures and withdraw from the study at any time.

12.3 Risks and Benefits of Study Procedures

There are minimal risks to the participant during this trial. Participants may experience some mild or rare side effects as described in Chapter 7 due to the treatment. Adverse effects will be monitored. If any question on the questionnaire makes the participant uncomfortable, and they do not wish to answer, then they may skip the question. The patient may withdraw from the study at any time.

The swabbing procedures present minimal risk to the study participants as well. The participants will self collect a nasal, saliva, and rectal swab. Temporary discomfort may occur. Adverse events such as nose bleeds are possible, but uncommon.

13 Study Monitoring

The project will be continuously monitored by the supervisory team, which will consist of members from UCSF. The supervisory team will run daily and weekly monitoring reports.

The study analyst will daily update the list of eligible participants based on the REDCap screening form. The coordinator will then contact these eligible participants to explain the study in detail, collect informed consent, and obtain the participant's place of residence. The analyst will also inform the coordinator of participants who are late in filling out their questionnaires so that the coordinator may follow-up with them.

A weekly data quality report will be sent to the entire supervisory team, which will include enrollment counts, follow-up data, primary outcome data, and other study statistics.

13.1 Protocol Violations

A protocol violation occurs when the subject, investigator, or study staff fails to adhere to significant protocol requirements affecting the inclusion, exclusion, subject safety and primary endpoint criteria. Protocol violations for this study include, but are not limited to, the following:

- Failure to meet inclusion/exclusion criteria
- Changes in the conduct of the research protocol without prior IRB approval
- Any violation that has harmed, or posed significant risk of harm, to the research participant

Failure to comply with Good Clinical Practice (GCP) guidelines will also result in a protocol violation. When a protocol violation occurs, it will be discussed with the investigator and a Protocol Violation Form detailing the violation will be generated. This form will be signed by a Sponsor representative and the Investigator. A copy of the form will be filed in the site's regulatory binder and in the Sponsor's files for FDA reporting purposes. Any protocol violation must be reported the UCSF IRB as well.

14 Data Collection, Management, and Security

The project will be continuously monitored by the supervisory team, which will consist of members from the UCSF F.I. Proctor Foundation. The supervisory team will communicate with participants and monitor the data daily. This section discusses how the data are collected, entered into the database, stored, and transferred to the Data Coordinating Center under the supervision of [name].

14.1 Scope of the Data

Mortality and morbidity data will be collected in this trial. Participant vital status will be collected at day 3, day 7, day 14 and 21 day follow-ups. Hospitalization and COVID-19 status will also be collected during follow-ups via an electronic questionnaire.

14.2 Data Storage, Management, and Security

Data will be recorded electronically using REDCap. Data will be stored in a secure directory on Box, which maintains HIPAA-level compliance and encryption for UCSF accounts (details here: <https://it.ucsf.edu/services/ucsf-box/additional/how-does-box-protect-your-data>). Rapid transfer of electronically captured data will allow nearly real-time monitoring of activity at the study site. All handheld devices and data entry coordinating centers will be password protected, and all changes in data will be noted, including the date of the change, and the person who made the change. All information collected will adhere to HIPAA compliance rules.

14.3 Electronic Data Collection Forms

All forms for this study will be created electronically on REDCap. These forms will be tested by the UCSF investigators prior to using them for the study. All REDCap forms are electronic and should be completed in their online version. Paper copies will be available to be downloaded, printed, and completed by hand if necessary, but electronic data entry is preferred. Study personnel should communicate any clarifications or updates to the study forms to all participants.

